### 9.5.1.1. Study Monitoring

**Table 8: Specification of Sequential Statistical Analyses**

Parameter	Population	Hypothesis	Statistical Method	Criterion	Monitoring Plan
Potential Harm a of Symptomatic Cases	FAS	$H_0: VE \geq 0\%$ vs. $H_1: VE < 0\%$	Exact 1 sided binomial test of the fraction of infections assigned to who receive the vaccine.	Constant p value cut off controlling $\alpha$ at 5%	After every event starting from the 12 th event b
Potential Harm a of Severe Cases	FAS	$H_0: VE \geq 0\%$ vs. $H_1: VE < 0\%$	Exact 1 sided binomial test of the fraction of infections assigned to who receive the vaccine.	Unadjusted p value $\alpha$ at 5%	After every event starting from the 5 th event
Non efficacy	PP	$H_0: VE \geq 40\%$ vs. $H_1: VE < 40\%$	Exact 95% CI	Upper limit of the 95%CI $< 40\%$	Every 2 weeks, starting from the 20 th event after 14 days following double blind vaccination (Day 15) b
Efficacy	PP	$H_0: VE \leq 50\%$ vs. $H_1: VE > 50\%$	Sequential probability ratio test	Controlling the family wise error rate $\alpha$ at 2.5%	Starting from the 42 nd event c 14 days following double blind vaccination (Day 15), then at least once a week
Efficacy	PP	$H_0: VE \leq 30\%$ vs. $H_1: VE > 30\%$	Sequential probability ratio test	Controlling the family wise error rate $\alpha$ at 2.5%	Starting from the 42 nd event c 28 days following double blind vaccination (Day 29), then at least once a week

CI confidence interval; FAS full analysis set; PP per protocol; VE vaccine efficacy.

a Harm in the form of an increased rate of symptomatic COVID 19 events due to vaccination (which meet the mild, moderate or severe/critical case definition).

b Monitoring stops when the primary efficacy analysis is triggered.

c The monitoring can only start as soon as the conditions outlined in Section 9.5.1 are met.

All boundaries will be monitored by an SSG. Once a boundary has been crossed, the SSG will inform the DSMB and a DSMB meeting will be organized. The statistical details of the decision rules and the frequency of evaluation and operational implementation will be fully detailed in the SAP and DSMB Charter.

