## 9.2. Sample Size Determination

### 9.2.1. Efficacy (Total Sample Size)

The study TNE is determined using the following assumptions:

- a VE for molecularly confirmed, moderate to severe/critical SARS-CoV-2 infection of 60%.
- approximately 90% power to reject a null hypothesis of  $H_0: VE \leq 30\%$ .
- type 1 error rate  $\alpha = 2.5\%$  to evaluate VE of the vaccine regimen (employing the sequential probability ratio test [SPRT] to perform a fully sequential design analysis; detailed in Section 9.5.1).
- a randomization ratio of 1:1 for active versus placebo

Events are defined as first occurrence of molecularly confirmed, moderate to severe/critical COVID-19 according to the case definition in Section 8.1.3.1 in the PP population. The two co-primary endpoints will evaluate the events at least 14 days after double-blind vaccination (Day 15) and at least 28 days after double-blind vaccination (Day 29) with study vaccine.

Under the assumptions above, the TNE to compare the active vaccine versus placebo equals 154, based on events in the active vaccination and placebo group, according to the primary endpoints case definition of moderate to severe/critical COVID-19 (Section 8.1.3.1).

If the co-primary hypothesis testing is successful for both co-primary endpoints, secondary objectives will be evaluated against a null hypothesis employing a lower limit  $VE > 0\%$ . The

method to perform hypothesis testing of primary and secondary objectives preserving the FWER will be specified in the SAP. The FWER will be controlled at 2.5%.

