##### **9.5.1. Primary Endpoints Evaluation**

The study is designed to test the co-primary hypotheses of VE in the PP population. For both co-primary endpoints the following hypothesis will be tested:

H0: VE  $\leq 30\%$  versus H1: VE  $> 30\%$  and each hypothesis will be evaluated at a 2.5% one-sided significance level.

The co-primary endpoints will evaluate:

- the first occurrence of molecularly confirmed, moderate to severe/critical COVID-19 according to the case definition in Section 8.1.3.1, with onset at least 14 days after double-blind vaccination (Day 15) with Ad26.COV2.S versus placebo, in the PP population, including all events from both age groups, with and without comorbidities.
- the first occurrence of molecularly confirmed, moderate to severe/critical COVID-19 according to the case definition in Section 8.1.3.1, with onset at least 28 days after double-blind vaccination (Day 29) with Ad26.COV2.S versus placebo, in the PP population, including all events from both age groups, with and without comorbidities.

Participants included in the seronegative analysis set are those participants with a negative SARS-CoV-2 serology test result at (double-blind) baseline.

Considering the current COVID-19 pandemic, early detection of VE will be very important. The proposed current analysis setup is designed for continuous sequential analyses (see Section 9.5.1.1), where statistical hypothesis testing is conducted repeatedly on accumulating data, generating an earliest possible signal if and when the splits between the number of events in placebo recipients are much larger compared to the Ad26.COV2.S-vaccinated group for both co-primary endpoints and in such a way that they are unlikely to be due to chance alone using a truncated SPRT. A successful primary efficacy conclusion will require:

1. Establishing the hypothesis H1: VE  $> 30\%$  for each co-primary endpoint

AND

2. A favorable split vaccine:placebo for the subset of primary endpoints meeting the severe/critical COVID-19 case definition (expressed as a VE point estimate against severe/critical COVID-19 molecularly confirmed endpoints  $\geq 50\%$ ) and a minimum of 5 events in the placebo group. This requirement needs to be met for severe/critical events with onset at least 14 days after double-blind vaccination and for severe/critical events with onset at least 28 days after double-blind vaccination.

AND

3. A VE of at least 50% for each co-primary endpoint.

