To evaluate the primary null hypotheses: H0: VE  $\leq 30\%$  versus H1: VE  $> 30\%$  for the co-primary endpoints, the truncated sequential probability ratio test will be used based on accumulating event data for each co-primary endpoint. This boundary is set up using the fully sequential design and is derived in such a way to have approximately 90% power to detect a VE 60% using a one-sided alpha 0.025 against H0:VE  $\leq 30\%$ . For the evaluation of the favorable ratio against the severe/critical COVID-19 endpoints a sequential boundary corresponding to a VE point estimate

$\geq 50\%$  and a minimum of 5 events in the placebo group will be prespecified. The specific boundaries will be detailed in the SAP.

The monitoring can start as soon as the following conditions are met:

1. A minimum of 6 COVID-19 cases for the  $\geq 60$  years age group with onset at least 28 days after double-blind vaccination
2. At least 42 cases meeting the primary endpoints definition of moderate to severe/critical COVID-19 with onset at least 28 days after double-blind vaccination
3. A subset of at least 5 cases meeting the primary endpoints definition of severe/critical COVID-19 with onset at least 28 days after double-blind vaccination

No interim evaluation will be done, until those conditions are fulfilled. Monitoring for efficacy will not start before the above conditions 1-3 are met and will occur at least once a week by the SSG of the DSMB until the prespecified boundaries have been crossed.

The efficacy analysis will be triggered by either:

1. a) An interim evaluation if all prespecified efficacy boundaries have been met OR if 154 cases meeting the primary endpoints definition of moderate to severe/critical COVID-19 are observed for events with onset at least 28 days after double-blind vaccination

AND

1. b) The above 3 conditions are met.

OR, alternatively,

2. If the prespecified non-efficacy boundary has been met (evaluating events with start 28 days after double-blind vaccination) or when the harm boundary has been crossed. The decision rules for harm and non-efficacy are detailed in Section 9.5.1.1.

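### Table 8 gives the Day 15 co-primary endpoint a null of VE ≤ 50%, contradicting the 30% null that Sections 9.2.1 and 9.5.1 set for both co-primary endpoints

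*Protocol*

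**What the plan says.** **Section 9.2.1** derives the target number of events from "a VE for molecularly confirmed, moderate to severe/critical SARS-CoV-2 infection of 60" per cent and "approximately 90% power to reject a null hypothesis of" VE ≤ 30%, at 2.5% type 1 error and 1:1 allocation. The result is 154 events.

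**Section 9.5.1** introduces its null with the words "For both co-primary endpoints the following hypothesis will be tested" and gives VE ≤ 30% against VE > 30%; "each hypothesis will be evaluated at a 2.5% one-sided significance level". Success criterion 1 is VE > 30% for each co-primary endpoint. Success criterion 3, listed separately, asks for a VE of at least 50% on each. The section describes the truncated SPRT boundary as "derived in such a way to have approximately 90% power to detect a VE 60% using a one-sided alpha 0.025", again against VE ≤ 30%.

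**Table 8 in Section 9.5.1.1** has two efficacy rows, both in the PP population and both using the SPRT.
- The row monitored from "14 days following double blind vaccination (Day 15), then at least once a week" has the hypothesis "H_0: VE \leq 50\%$ vs. $H_1: VE > 50" per cent.
- The row for onset from Day 29 has "H_0: VE \leq 30\%$ vs. $H_1: VE > 30" per cent.

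**The concern.** The null hypothesis of a co-primary endpoint is stated in two incompatible ways in current text. The choice is not cosmetic. It fixes the Day 15 stopping boundary, the observed efficacy needed to cross it, and the claim that a positive result supports (VE above 30% or above 50%).

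Both co-primary endpoints must succeed, and an early efficacy signal requires every prespecified efficacy boundary to be met. A Day 15 boundary built on 50% would therefore become the limiting condition for the whole trial. Table 8 is headed as the specification of the sequential analyses, so someone programming from it could reach a different boundary from someone programming from Section 9.5.1.

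**Working it through.** **Inputs**
- Planned VE 60%, 1:1 allocation, one-sided 2.5%, 154 events (Section 9.2.1).
- Test model (Section 9.5.1.1): given T events in total, vaccine cases X2 are binomial(T, π) with π = (1 − VE)/(2 − VE).
- Null of 30% (Sections 9.2.1 and 9.5.1) or 50% (Table 8, Day 15 row).

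**Values of π**
- VE 30%: 0.7/1.7 = 0.4118
- VE 50%: 0.5/1.5 = 0.3333
- VE 60%: 0.4/1.4 = 0.2857

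**Rule.** The critical value C is the largest integer with P(X2 ≤ C | T, π0) ≤ 0.025. Power is P(X2 ≤ C | T, 0.2857).

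**Step 1: reproduce the protocol's figure.** With π0 = 0.4118, the smallest T with power of at least 90% is 154. There C = 51, the attained size is 0.0246 and power is 0.908. The 154-event target therefore rests on the 30% null.

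**Step 2: same event count, Table 8 null.** With π0 = 0.3333 and T = 154, C = 39, the size is 0.0198 and power is 0.212. The observed VE at the limit is 1 − 39/115 = 66%, against 1 − 51/103 = 50.5% in step 1.

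**Step 3: more Day 15 events.** The 154-event trigger counts events with onset at least 28 days after vaccination, so the Day 15 count is then at least 154. Its size is not stated. The counts above 154 below are assumptions.

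| Day 15 events | C, null 50% | Observed VE at C | Power at VE 60% |
|---|---|---|---|
| 154 | 39 | 66% | 21% |
| 185 (assumed) | 48 | 65% | 24% |
| 220 (assumed) | 59 | 63% | 31% |
| 250 (assumed) | 68 | 63% | 34% |
| 300 (assumed) | 83 | 62% | 39% |

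For 90% power against the 50% null, the same rule needs 998 events.

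**Step 4: like-for-like sequential check.** We used a linear SPRT-type boundary with VE 60% as the alternative, a first look at event 42, a look after every event, truncation at 154, and calibration to at most 2.5% overall. Power is about 83% for the 30% null and about 21–22% for the 50% null. This is our boundary, not the sponsor's, which the protocol leaves to the SAP. It shows only that the gap persists when both nulls are treated sequentially.

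**Step 5: can success criterion 3 explain the row?** At 154 events, an observed VE of at least 50% allows up to 51 vaccine cases, because 52 gives 1 − 52/102 = 49%. Rejecting VE ≤ 50% allows only 39. These are different rules. Criterion 3 also covers both co-primary endpoints, whereas Table 8 puts 50% on Day 15 alone.

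**The case against.** The strongest reply is that one table cell stands against everything else. Section 9.2.1, the opening of Section 9.5.1, success criterion 1, the boundary description and the 154 events all point to 30%. The operating boundaries are deferred to the SAP and DSMB Charter, and neither document was available for this check. Section 3, to which Section 9.1 refers for the hypotheses, was also not seen. On this view the row is a slip with no consequence. That much stands: nothing here shows that a boundary with a 50% null was ever used.

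A reader might go further and infer that the trial had only 21% to 39% power, or that a vaccine with 60% efficacy would usually have failed. The documents do not support that. The loss follows only if the Table 8 row set the Day 15 boundary, and all figures above 21% depend on assumed Day 15 event counts.

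It is also fair that this text is at Amendment 7. The amendment history refers to results of the primary analysis and to use under emergency authorisation, so the choice of boundary is no longer a future risk to monitoring.

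Deferral to the SAP does not remove the contradiction. The protocol itself fixes the null, and fixes it twice. Whichever boundary the SAP contains for Day 15 must disagree with one of the two places.

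**Conclusion.** The Day 15 efficacy row of Table 8 is wrong as written when read with Sections 9.2.1 and 9.5.1. The inconsistency is certain. Which value was intended is very likely 30%, because the event target reproduces only with that null.

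The consequence is conditional. If Section 9.5.1 governs, planned power is unaffected. If the Table 8 row were used, single-look power at the planned VE would drop from 91% to 21% at 154 Day 15 events. It would remain below 40% at every assumed count up to 300. The 91% and 21% come from the protocol's own inputs and the exact binomial model.

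**What to change.** Change the Day 15 efficacy row of Table 8 to VE ≤ 30% against VE > 30%, matching the Day 29 row and Sections 9.2.1 and 9.5.1. Keep 50% only as success criterion 3. Confirm that the Day 15 boundary in the SAP and DSMB Charter uses π0 = 0.7/1.7 = 0.4118.

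This costs one table cell and one check of the boundary.

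If a 50% null was intended for Day 15, the change is much larger. Sections 9.2.1 and 9.5.1, the 154-event target and the stated power of about 90% would all need to be restated.

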### Sequential Probability Ratio Test

Following the notation of Dragalin et al. (2002) and Dragalin and Fedorov (2006), consider,  $X_1$  and  $X_2$  the number of events in respectively the placebo group and the vaccine group. The distribution of  $X_1$  and  $X_2$  can be approximated by a Poisson distribution with the following parameters:  $\lambda_i = n_i p_i$  (with  $i = 1,2$ ). Thus, the conditional distribution of  $X_2$  given  $T = X_1 + X_2 = t$  approximately follows a binomial distribution with parameters  $(t, \pi)$ , where  $\pi = \frac{\lambda_2}{(\lambda_1 + \lambda_2)} = \frac{n_2 p_2}{n_1 p_1 + n_2 p_2} = \frac{1 - VE}{2 - VE}$ , with  $VE = 1 - RR$ ,  $RR = \frac{p_2}{p_1}$ , assuming a vaccine group allocation ratio of 1:1. Consequently, testing the null hypothesis  $H_0: VE = VE_0$  against  $H_1: VE = VE^*$  is equivalent to testing  $H_0: \pi = \pi_0$  against  $H_1: \pi = \pi^*$  the conditional binomial test.

Consider  $\alpha = P(\text{reject } H_0 | VE = VE_0)$  and  $\beta = P(\text{accept } H_0 | VE = VE^*)$ . Rejecting  $H_0$  occurs when  $X_2 \leq C_\alpha$  with  $C_\alpha = C_\alpha(T)$  calculated to preserve  $\alpha$  over all the sequential looks such that

$P(X_2 \leq C_\alpha | \pi = \pi_0) = B(C_\alpha; T, \pi_0) \leq \alpha$ . With  $B(\cdot; T, \pi)$  the cumulative binomial distribution function with parameter  $T$  and  $\pi$ . The solution to the above equation,  $T^*$ , is the smallest  $T$  such that  $B(B^{-1}(\alpha; T, \pi_0); T, \pi^*) \geq 1 - \beta$ , with  $B^{-1}(\alpha; T, \pi)$  the  $\alpha$ -quantile of the cumulative binomial distribution function with parameters  $T$  and  $\pi$ .

The implemented critical boundaries for success are based on the truncated SPRT for which success boundaries are set based on observing  $X_2$  events on the vertical axis out of total  $T$  events on the horizontal axis.

### 9.5.2. Secondary Endpoints

All secondary endpoint analyses will occur in the PP analysis set, in seronegative participants unless otherwise indicated.

To evaluate the effect of the vaccine against symptomatic molecularly confirmed COVID-19, including mild infections, a BOD endpoint will be evaluated based on the first occurrence of molecularly confirmed COVID-19, including mild, moderate and severe/critical case definitions in Sections 8.1.3.1 and 8.1.3.2, with onset at least 14 days after double-blind vaccination (Day 15) and with onset at least 28 days after double-blind vaccination (Day 29) with Ad26.COV2.S versus placebo, in the PP population, including all events across age groups, with and without comorbidities. In this study, the BOD endpoint is defined as taking the value 1 for mild and moderate disease and the value 2 for severe disease (implicitly assigning a value of 0 for no disease [not infected or asymptomatic infection]). By assigning higher weight to severe infections, the BOD endpoint aims at providing higher statistical power for differentiating from placebo vaccines with increased protection against severe infections (but potentially lower vaccine efficacy against milder infections). The BOD evaluates the severity-adjusted VE against preventing symptomatic incidence. The hypothesis to evaluate the vaccine efficacy against symptomatic infection will be based on this method. In addition, the VE against each severity category according to the case definition (severe, moderate, mild) will be summarized separately. Statistical significance for the BOD endpoint will be tested using  $H_0: VE \leq 0$  at a one-sided  $\alpha = 2.5\%$  according to multiplicity adjusted strategy.

Details on the calculation of VE for the BOD endpoint and its associated confidence interval (for testing) and hypothesis testing will be foreseen in the SAP.

VE against severe/critical infections with onset at least 14 days after double-blind vaccination (Day 15) and with onset 28 days after double-blind vaccination will be evaluated. Exact Poisson regression will be used to estimate the VE and associated confidence interval in seronegative participants in the PP analysis set.

The co-primary endpoints and BOD endpoint will be evaluated at the time of efficacy signal, and again at the time when the 8-week median follow-up requirement is reached (should the efficacy signal occur earlier).

VE against any SARS-CoV-2 infection and against asymptomatic infections will be evaluated as soon as a sufficient number of participants have data available. This timepoint will be detailed in

the Statistical Analysis Plan and may occur at any of the planned analysis timepoints. Available N-serology measurements will be incorporated to evaluate VE against any infection, including asymptomatic infection and against asymptomatic/undetected infection only. A participant will be defined as having any infection whether he/she had either a symptomatic infection (mild, moderate or severe according to the case definition) or an asymptomatic infection (as defined in Section 8.1.3.4). Poisson regression will be used to estimate the VE and associated confidence interval in seronegative participants in the PP analysis set for each of both analyses.

Among participants with SARS-CoV-2 infection, the effect of the study vaccine on the viral load levels at and after diagnosis as well as on the duration of SARS-CoV-2 viral load positivity will be evaluated.

The effect of the vaccine will be evaluated against molecularly confirmed COVID-19 infections requiring medical intervention once sufficient events are available for events with onset at least 14 days after double-blind vaccination and with onset at least 28 days after double-blind vaccination. Medical interventions are evaluated as a composite endpoint of hospitalization, ICU admission, mechanical ventilation and ECMO, linked to objective measures such as decreased oxygenation, X-ray or CT findings. Exact Poisson regression will be used to estimate the VE and the associated confidence interval in seronegative participants in the PP analysis set.

All VE evaluations will be repeated regardless of their serostatus.

Supportive and/or descriptive analysis will be reported with 95% confidence intervals; confirmatory endpoints will have an adjusted confidence interval reported at the time of hypothesis testing whereby the alpha level is determined according to the FWER-controlled testing strategy.

The statistical analysis for secondary endpoints, multiple testing strategy to evaluate the secondary objectives, and the timing of the hypothesis testing will be detailed in the SAP.

See also Section 9.5.1.

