***Closure of the COVID-19 episode***

The participant should continue the COVID-19 procedures until any of the following occurs, based on molecular test results:

If both nasal swabs (collected on COVID-19 Day 1-2 and COVID-19 Day 3-5) are **negative** for SARS-CoV-2, the participant will not undertake any further COVID-19 procedures and will fall back to the default Schedule of Activities, until the end of the study/early withdrawal.

If the participant has at least 1 SARS-CoV-2 positive nasal swab collected on COVID-19 Day 1-2 or Day 3-5 visits, then the participant will be asked to undertake the COVID-19 procedures (2-day cycles) until 14 days after symptom onset (COVID-19 Day 15) or until **resolution of the COVID-19 episode**, whichever comes lasta. Resolution of the COVID-19 episode is defined as having 2 consecutive SARS-CoV-2 negative nasal swabs and 2 consecutive days with no COVID-19-related signs or symptoms. Once past COVID-19 Day 15, participants should stop the collection of nasal swabs and saliva samples as soon as 2 consecutive nasal swabs are SARS-CoV-2 negative, but (if still symptomatic at that time) should continue completing the ePROs (including SIC, body temperature, and pulse oximetry) in the eCOA until 2 consecutive days with no COVID-19-related signs or symptoms.

*Note:* for participants who have signs and symptoms present at baseline (assessed pre-vaccination), only signs and symptoms that are associated with COVID-19 and that developed during the COVID-19 episode are to be taken into account.

If signs and symptoms are still ongoing on **COVID-19 Day 3-5**, collection of SIC will be continued until at least 14 days after onset unless both **COVID-19 Day 1-2** and **COVID-19 Day 3-5** are both negative. If either of the swabs is positive or the result is unknown AND the participant is beyond 14 days after onset of symptoms, the SIC can be stopped after 2 days without signs and symptoms.

If 2 consecutive nasal swabs negative for SARS-CoV-2 are not available due to operational reasons (eg, delays in results availability), participants may cease collection of nasal swabs and saliva samples after COVID-19 Day 29, provided they have 2 consecutive days with no COVID-19-related signs and symptoms. In these cases, participants may be asked to resume sample collection if nasal sample results once available do not present with 2 consecutive negative swabs for SARS-CoV-2.

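### The vaccine effect on viral load and duration of positivity is evaluated only among infected participants, a subset the vaccine itself changes, so the contrast is not randomised and may reflect selection

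*Protocol*

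**What the plan says.** Section 9.5.2 of the protocol gives the viral load analysis one sentence. It opens "Among participants with SARS-CoV-2 infection, the effect of the study vaccine on the viral load levels at and after diagnosis" and ends "as well as on the duration of SARS-CoV-2 viral load positivity will be evaluated". This fixes two things: the population (infected participants) and the target (an effect of the vaccine). The general rule for the section is "All secondary endpoint analyses will occur in the PP analysis set, in seronegative participants unless otherwise indicated". Nothing there adds uninfected participants to this endpoint.

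Other endpoints in the same section do count prevented cases. The burden-of-disease (BOD) endpoint keeps every participant by "implicitly assigning a value of 0 for no disease". Efficacy against any infection, asymptomatic included, is estimated in seronegative per-protocol participants.

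Sampling also depends on what happens after vaccination. Apart from the routine baseline and Month 6/Unblinding swabs, swabs are triggered by symptoms or by a positive test obtained outside the study (Sections 8.1.1 and 8.1.2.2). Under the rules for closing an episode, two-day sampling runs to resolution only "If the participant has at least 1 SARS-CoV-2 positive nasal swab collected on COVID-19 Day 1-2 or Day 3-5 visits".

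**The concern.** Randomisation makes the two groups comparable as enrolled. It does not make those who later became infected comparable if the vaccine decides who enters that group. An efficacious vaccine leaves in its infected group only those it failed to protect. If they had higher exposure or weaker immunity and so tend to higher loads, a vaccine with no effect on load appears to raise it, and a true reduction is diluted. If the vaccine more readily stops high-load infections, a false reduction appears.

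Triggered swabbing may add to this. If vaccination makes infections milder, fewer are detected and followed, and the observed infected vaccinees are selected a second time.

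At stake is the reading of a secondary result. A selected contrast could be reported as what the vaccine does, or fails to do, to viral load and its duration.

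**Working it through.** **1. The protocol's own figure.** Section 9.2.1 gives a target of 154 events, for 60% efficacy against moderate to severe/critical disease, a null of 30%, one-sided alpha 2.5%, about 90% power and 1:1 allocation. Section 9.5.1.1 gives the share of cases in the vaccine group as π = (1 − VE)/(2 − VE).
- Null: 0.7/1.7 = 0.4118. Alternative: 0.4/1.4 = 0.2857.
- The smallest total with exact one-sided alpha ≤ 0.025 and power ≥ 0.90 is 154 (reject at 51 or fewer vaccine cases; alpha 0.0246, power 0.908). The figure reproduces and is not in dispute.

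**2. What an infected-only comparison leaves out.** These 154 cases serve as an illustration, since they are moderate to severe/critical cases and not all infections.
- Vaccine cases: 154 × 0.2857 = 44. Placebo cases: 154 − 44 = 110.
- Absent from the vaccine side: 110 − 44 = 66.
- If the vaccine causes no infections, 44/110 = 40% of the placebo cases are of the kind that would also have been infected on vaccine. Which ones they are is not observable.

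**3. Worst-case bound with no true effect on load.** Assume a normal load distribution and no infection caused by the vaccine. Infected vaccinees then correspond to a fraction 1 − VE of the infected placebo group. The extreme case is that this is exactly the top or bottom 1 − VE of loads. The shift in mean, in SD units, is φ(z)/(1 − VE), where z is the standard normal quantile at VE. Efficacy against any infection is not stated, so two assumed values are shown.
- VE 30%: φ(0.524)/0.7 = 0.348/0.7 ≈ 0.50 SD.
- VE 60%: φ(0.253)/0.4 = 0.386/0.4 ≈ 0.97 SD.

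Either sign is possible.

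**4. Less extreme selection.** Let the odds of breaking through rise by a fixed factor per SD of load. The factors are assumed and come from nowhere in the protocol.

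| Odds ratio per SD | VE 30% | VE 60% |
|---|---|---|
| 1.00 | 0 | 0 |
| 1.25 | 0.07 SD | 0.13 SD |
| 1.50 | 0.12 SD | about 0.23 SD |
| 2.00 | 0.19 SD | 0.38 SD |

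**5. What an all-participant burden score would show.** With equal arms, uninfected scored 0 and load per infection unchanged, the ratio of mean burden is 1 − VE: 0.70 at 30% and 0.40 at 60%. The score counts prevented infections but is driven mainly by efficacy against infection.

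**The case against.** The strongest reply has four parts.

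- Section 9.5.2 defers the statistical analysis of secondary endpoints to the SAP, and Section 9.5 calls itself a summary. Models, bounds and sensitivity analyses belong in the SAP. That stands for method detail. It does not undo a sentence that already fixes an infected-only population and calls the result an effect of the vaccine.
- The conditioning is disclosed in the opening words, no hypothesis or test is given for this endpoint, and nothing shown makes it confirmatory. That stands and limits the weight of the point. Disclosing the subset still does not say that the contrast is non-randomised.
- Prevented infections are counted in the analysis of efficacy against any infection, and load given infection is a legitimate question. That stands. A reader might infer that a zero-filled burden score should replace the infected-only analysis. The protocol does not support this: the score would largely repeat the efficacy result and would not answer the question posed.
- An all-participant score has its own weaknesses. The per-protocol set is not as randomised, because participants who learn their allocation leave it (Section 9.3). Infections found only by N-serology (Section 8.1.3.4) may have no measured load. Both stand, and the fix has to deal with them.

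A reader might also infer that the viral load result will be biased by close to 1 SD, or against the vaccine. The protocol supports neither. The 60% refers to moderate to severe/critical disease, and the bound requires load alone to determine breakthrough.

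**Conclusion.** The point holds in a limited form. As written, Section 9.5.2 presents as a vaccine effect a comparison within a subset defined after randomisation and altered by the vaccine. The result may therefore mix selection with any real effect on load or duration.

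The amount and direction cannot be derived from the protocol. With no true effect on load, the bias is zero if breakthrough is unrelated to load. At the extreme it is about 0.50 SD at 30% efficacy against infection and about 0.97 SD at 60%. These bounds rest on assumed efficacies, a normal load distribution and no vaccine-caused infections.

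It would go too far to conclude that no caveat or supplementary analysis exists anywhere, since Section 3 and the SAP are outside the text considered here. The co-primary endpoints, the success criteria and the primary conclusion are unaffected.

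**What to change.** In Section 9.5.2:

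1. Keep the infected-only comparison of viral load and duration, and state that it is descriptive, conditional on infection and non-randomised. Report it with principal-stratum (trimming) bounds computed from the observed efficacy against infection.
2. Add, as a supplement and not a replacement, a viral burden comparison in all seronegative participants (for example peak log10 load, or days positive) with uninfected participants scored 0. Run it in the per-protocol set and repeat it in the FAS.
3. State a sensitivity rule for infections detected by serology only that have no measured load, so that they are not silently scored as zero.

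The cost is a change of wording and a few extra tables from data already collected, with no change to sample size or visits. The drawback is that the burden score mainly reflects efficacy against infection and says little about load per infection, which is why the infected-only summary is retained.
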